5.6.3 Prior and Concomitant Therapies/ Medications

Prior Therapies/ Medications:

Prior Therapies/Medications include any therapy or medication with start date prior to the start of IMP application. They will be classified according to the World Health Organization Drug Dictionary (WHO-DD; version March 2022 Q) as prior medication.

Concomitant Therapies/ Medications:

Concomitant therapies/ medication will include therapies/ medications starting before or after the start of IMP application and continuing after the start of IMP application. They will be classified according to the WHO-DD; version March 2022 Q.

Descriptive summaries will be by WHO-DD Anatomical Therapeutic Chemical (ATC) level 2 and ATC level 4. There will be separate summaries for all prior therapies/ medications, prior therapies/ medications that were ongoing at baseline, and concomitant therapies/ medications. Prior and concomitant therapies/ medications will be listed by subject.

5.6.4 Adverse Events

Adverse events (AE) will be coded using MedDRA version 24.1 terminology. Treatmentemergent adverse events (TEAEs) related TEAEs (unlikely related, possibly related, and probably related), non-serious TEAEs, serious TEAEs (TESAEs), related TESAEs, TEAEs leading to treatment discontinuation or trial withdrawal, and deaths will be summarized for the overall incidence of at least one event, incidence by SOC and incidence by SOC and PT.

By definition, TEAE is an AE that began after the start of trial medication treatment. TESAE's are any TEAE's that are reported as serious in the eCRF.

Each subject will contribute only once to each of the incidence rates, regardless of the number of occurrences (events) the subject experiences. The number of occurrences for each SOC and PT will also be displayed.

TEAEs will also be descriptively summarized by severity (mild, moderate or severe) and by relationship to IMP [not related or related (unlikely related, possibly related and probably related)]. In summaries of severity and relationship, subjects who report more than one event mapped to the same SOC or PT will be counted only once under the strongest severity and relationship, accordingly.

An AE is treatment-emergent if its date of onset in on or after the first application date of IMP. An AE is related if relationship to IMP is assessed as unlikely related, probably related, or possibly related.

TEAEs, TESAEs, TEAEs leading to treatment discontinuation or study withdrawal and deaths will be listed by subject.

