- 11. Vital signs include blood pressure, heart rate, and body temperature measurement. For subjects on haemodialysis vital signs are to be assessed prior to dialysis. Blood pressure and pulse rate will be taken with the subject in the sitting position with approximately 5 minutes rest prior to measurement.
- 12. Serum pregnancy tests are conducted for women of childbearing potential. At Baseline a urine pregnancy test must also be conducted except for dialysis subjects with anuria.
- 13. For subjects on dialysis, the blood samples must be collected before dialysis.
- 14. Only at selected sites and only for subjects who have provided additional consent. CKD-aP target area selected at Baseline. Images of CKD-aP target area must be taken before tape stripping and skin biopsies.
- 15. Only at selected sites and only for subjects who have provided additional consent. Biopsy: 4 mm skin punch biopsy (optional) is taken from the CKD-aP target area.
- 16. Tape stripping is conducted in all subjects from the CKD-aP target area.
- 17. "Therapies" refers to medications and therapies.
- 18. The first IMP application shall preferably be performed in the clinic under surveillance, and assistance if necessary, of trial staff.

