7.6 Electrocardiogram (ECG)

A single 12-lead ECG must be recorded using local equipment at Baseline, Week 4, and Week 12 or Early Termination. For subjects with ongoing SAEs or related AEs at Week 12, a single 12-lead ECG will also be performed at Week 14 (Follow-up) if judged necessary by the investigator. In haemodialysis subjects, ECGs are to be performed preferably prior to dialysis. Interpretation of ECGs will be based on machine read-out and local physician evaluation (cardiologist overread will not be performed).

Any abnormalities must be assessed as "clinically significant" or "not clinically significant" by the investigator. Abnormalities classified as "clinically significant" must be recorded in the eCRF as AEs except those observed at Screening visit 1, which will be recorded as medical history.

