8.7.1 Adverse events

Adverse events will be coded using Medical Dictionary for Regulatory Activities (MedDRA) terminology. Treatment-emergent adverse events (TEAEs), related TEAEs, non-serious TEAEs, serious TEAEs, related serious TEAEs, TEAEs leading to treatment discontinuation and Deaths

will be summarised by the overall incidence of at least one event, incidence by body system, and incidence by body system and preferred term. Each subject will contribute only once (e.g., the first occurrence) to each of the rates, regardless of the number of occurrences (events) the subject experiences. The number of occurrences will also be displayed.

Treatment-emergent AEs will be summarised by severity (mild, moderate, or severe), and by relationship to trial product (not related, unlikely, possibly, or probably). In summaries of severity and relationship, subjects who report more than one event that are mapped to the same preferred term will be counted only once under the strongest severity and relationship, accordingly. An AE is treatment-emergent if its date of onset is on or after the day of start of trial medication. An AE is related if relationship to trial product is not assessed as unrelated.

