5.6.1 Product Compliance

Subjects enrolled in the trial are required to apply the IMP twice daily during the 12 week double-blind treatment period starting on the day of randomization (Baseline) and ending on the Week 12 visit date (End of Treatment). The total number of IMP applications and the number of missed applications during this period is recorded in the Treatment Application Record on a daily basis and entered in the eCRF.

The applications compliance rate for each subject is defined as:

Compliance = (Actual number of applications in treatment period / Number of expected applications in treatment period) * 100.

Where;

Actual number of applications in treatment period = Total number of applications applied during the course of the trial as reported in the eCRF

Number of expected applications in treatment period = Total number of days from baseline visit (randomization) till Week 12 (EoT) or early withdrawal X 2 (Twice daily application) -2

Duration of treatment period = Total number of days from baseline visit (randomization) till Week 12 (EoT) or early withdrawal

Compliance will be summarized in following categories; less than 80%, \geq 80 to \leq 100% and >100% (in cases where subject used the medication more than prescribed times a day) and average compliance in each treatment arm. Accumulated subject listings will also be presented for compliance.

100% compliance means the subject applied IMP twice daily as prescribed for total number of days in the trial and there were no missed applications between first and last application.

Descriptive statistics will be used to summarize product compliance for the SAS. Subject listing for compliance will be presented by 4-week periods (Baseline to < Week 4, \ge Week 4 to < Week 8, and \ge Week 8 and for overall trial period.

5.6.2 Drug Accountability and Extent of Exposure:

As a part of drug/product accountability, the amount of trial product dispensed and returned (used and unused) will be kept during the trial at each visit and at completion of the trial. Each dispensed kit consists of 5 tubes with each tube having a weight of 74.8 grams (tube with cream and label).

Subjects will return all used and unused tubes at Week 4, 8 and 12 visits and all returned tubes which have broken seals will be weighed to determine the residual amount of the IMP. The following averages will be calculated for all subjects as well as for subjects returning at least 80% of the IMP dispensed during the trial:

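### SAP 5.6.4 defines treatment-emergent in two ways, and its date rule can count clinically significant ECG abnormalities found before the first application as TEAEs

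*SAP*

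**What the plan says.** SAP 5.6.4 first states: "By definition, TEAE is an AE that began after the start of trial medication treatment". Further down the same section it states: "An AE is treatment-emergent if its date of onset in on or after the first application date of IMP". Protocol 8.7.1 has only the date version: "An AE is treatment-emergent if its date of onset is on or after the day of start of trial medication". The SAP's list of changes from the protocol (6.2) does not mention a change of definition.

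On what becomes an adverse event, protocol 7.6 says that clinically significant ECG abnormalities "must be recorded in the eCRF as AEs except those observed at Screening visit 1, which will be recorded as medical history". Sections 7.4, 7.5 and 7.8 apply the same rule to physical examination, vital signs and laboratory tests. The ECG schedule in 7.6 is: "A single 12-lead ECG must be recorded using local equipment at Baseline, Week 4, and Week 12 or Early Termination". The visit schedule (protocol Table 3) likewise shows no ECG at Screening, whereas the other three assessments are done at both Screening and Baseline.

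On timing, SAP 5.6.1 starts treatment on the day of randomisation, which is Baseline. The protocol's schedule notes add: "The first IMP application shall preferably be performed in the clinic under surveillance, and assistance if necessary, of trial staff". SAP 5.1 defines Baseline for safety summaries as the last observation before the first application. Protocol 7.12.1 lists start and stop dates among the adverse event items and names no onset time.

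**The concern.** The two sentences in 5.6.4 can disagree only about events dated on the day of first application. That day holds two different kinds of event: findings from assessments made before any cream is applied, and reactions to the first application. A rule that uses only dates cannot tell them apart.

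The ECG is the clearest case. The Screening exemption is what normally sends pre-existing disease to medical history, and it can never apply to a scheduled ECG. A long-standing abnormality first seen on the Baseline tracing can thus enter the adverse event tables as treatment-emergent, while the ECG shift tables (SAP 3.5) use the same tracing as the pre-treatment reference. The two outputs would contradict each other.

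Safety is the secondary objective, TEAE frequency is its first-listed endpoint, and this is the first use of the cream in humans. Protocol Table 1 offers the in-clinic first application as a mitigation for application site reactions, so events on that day need to be classified correctly.

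**Working it through.** The plan states no figure to reproduce. The check is a reading of the rules, followed by an illustration of size.

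**Step 1: does a pre-dose ECG finding become an adverse event?** The first scheduled ECG is at Baseline (protocol 7.6, Table 3), and the exemption covers Screening only. So yes, if the investigator judges the abnormality clinically significant. Normal tracings, and abnormal ones judged not clinically significant, do not become adverse events.

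**Step 2: when does that adverse event become a TEAE?** Take the first application to be on the Baseline day (SAP 5.6.1), and apply SAP 5.6.4 (date rule) and SAP 6.1 (partial dates):

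| Onset entered | Treatment-emergent? |
|---|---|
| Complete date, day of first application | Yes, date rule |
| Completely missing | Yes, SAP 6.1 |
| Day missing, same month and year as first application | Yes, SAP 6.1 |
| Year only, same year as first application | Yes, SAP 6.1 |
| Complete date before first application | No |

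Neither document says how to date the onset of a finding first seen at a visit.

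**Step 3: the other assessments.** Physical examination, vital signs and laboratory tests are also done at Screening, where clinically significant findings go to medical history. Mainly findings that are new at Baseline are exposed.

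**Step 4: the strict sentence.** Read as a sequence in time, it excludes pre-dose findings and keeps post-dose reactions, but the adverse event items listed in protocol 7.12.1 do not supply a time. Read as a comparison of dates, it would exclude everything dated on the day of first application, including true reactions to that application.

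**Step 5: size, by assumption.** Inputs are 72 cream and 36 vehicle subjects (protocol 8.2) and an assumed proportion p of subjects with an affected pre-dose finding. The documents give no value for p. The expected number is arm size × p. The chance of at least one in the trial is 1 − (1 − p)^108.

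| p (assumed) | Cream, 72p | Vehicle, 36p | Total, 108p | Chance of at least one |
|---|---|---|---|---|
| 1% | 0.7 | 0.4 | 1.1 | 66% |
| 3% | 2.2 | 1.1 | 3.2 | 96% |
| 5% | 3.6 | 1.8 | 5.4 | 99.6% |
| 10% | 7.2 | 3.6 | 10.8 | >99.9% |

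**Step 6: effect on the comparison.** Suppose, for illustration only, true TEAE rates of 30% on cream and 20% on vehicle, and an independent pre-dose rate of 5% in each arm. The reported rates become 1 − 0.70 × 0.95 = 33.5% and 1 − 0.80 × 0.95 = 24.0%. The ratio falls from 1.50 to 33.5/24.0 = 1.40, and the difference from 10.0 to 9.5 percentage points. At p = 10% the rates are 37.0% and 28.0%, a ratio of 1.32.

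**The case against.** The best defence is that the date rule agrees with protocol 8.7.1 and with the partial-date rules in SAP 6.1. The strict sentence can then be read as the general concept, with the date rule as its implementation. On that reading the programmer faces little real choice, and reactions after the first application are kept, since they did begin after treatment started. This stands. A reader might infer that the SAP loses first-application reactions, but that follows only if the strict sentence is turned into a comparison of dates, which the text does not do.

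It can also be said that the rule concerns onset and not detection. An earlier complete onset date escapes it, and current and recent conditions are collected as medical history (protocol 7.2). This stands too and narrows the exposed group. It does not remove it, because sites get no instruction on dating and SAP 6.1 treats an unknown onset as treatment-emergent.

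Third, the consequence is limited. A pre-dose finding fits the category of not related in protocol 7.12.4, shift tables are produced, and safety analysis is descriptive (SAP 5.6). Largely true, although SAP 5.6.4 counts a rating of unlikely related as related, so a finding rated that way would enter the related-TEAE table. The eCRF is not among the documents, so an onset time may be collected; even then, the date rule as written would not use it.

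**Conclusion.** Wrong as written, limited to descriptive safety reporting. SAP 5.6.4 carries two definitions that need to be one. Under the protocol-concordant rule, a clinically significant abnormality on the pre-dose Baseline ECG is counted as a TEAE whenever its onset is dated that day, missing, or partial in the same month or year. This rests on the first application falling on the Baseline calendar day and on the Baseline ECG preceding it, as SAP 5.6.1 and 5.1 imply.

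The size cannot be known from the documents. The range of about 1 to 11 of 108 subjects rests wholly on the assumed 1% to 10%.

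Three stronger readings are not supported. The plan does not turn every first ECG into a TEAE, only clinically significant abnormalities. It does not expose Baseline laboratory, vital-sign and examination findings to the same degree, because those have a Screening measurement. It does not bias the comparison against the cream: 2:1 allocation puts more of the affected subjects on cream, but the expected rate is the same in both arms. Alpha, power and the primary endpoint are unaffected.

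**What to change.** 1. In SAP 5.6.4, keep the date rule, which matches protocol 8.7.1, and delete the strict sentence or align it with the rule. Reactions on the day of first application then stay counted.
2. In protocol 7.4 to 7.8 and in the SAP, record clinically significant findings from Baseline assessments done before the first application as medical history. Alternatively, state that adverse events identified from pre-dose Baseline assessments are not treatment-emergent. A before/after-first-application flag for adverse events dated that day is one way to apply this.

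The cost is wording in both documents, including a protocol amendment under protocol 9.1 if sections 7.4 to 7.8 change, plus one eCRF item if the flag is used. If the protocol and eCRF cannot be changed, a rule in the SAP alone would cover the Baseline ECG, laboratory, vital-sign and examination findings; it should be listed in SAP 6.2 as a departure from protocol 8.7.1 and settled before database lock.

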7.12.4 Relationship of adverse events to trial treatment

The investigator is responsible for assessing the relationship of an AE to the IMP treatment using good clinical judgment and the following definitions:

- Not related The AE is clearly explained by another cause not related to the IMP administration; the temporal relationship of the AE to IMP administration makes a causal relationship clearly improbable or concomitant medication, therapeutics interventions, or underlying condition provide a sufficient explanation for the observed AE.
- Unlikely related The AE is most likely related to actiology other than the IMP administration; the temporal relationship of the AE to IMP administration makes a causal relationship unlikely, and other concomitant medication, therapeutic interventions or underlying disease provide plausible explanations for the observed AE.
- Possibly related The AE and administration of IMP are temporally related, but the AE can be explained equally well by causes other than the IMP administration. A causal relationship is conceivable and cannot be dismissed.
- Probably related The AE and use of IMP are temporally related, and the AE is more likely explained by IMP administration than by other causes. Good reason and sufficient documentation to assume a causal relationship.

The last relationship recorded during the course of an AE will be considered the final relationship as the investigator is assumed to have had the most information to perform the relationship assessment at that time.

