3.5 Safety Endpoints

- Frequencies of treatment-emergent adverse events (TEAEs), treatment-emergent serious AEs (TESAEs), treatment-related TEAEs (unlikely related, probably related, and possibly related), TEAEs leading to treatment discontinuation or trial withdrawal, and deaths during the trial for MC2-25 cream compared to MC2-25 vehicle.

- Mean change in vital signs (heart rate (HR), systolic blood pressure (SBP), diastolic blood pressure (DBP), and body temperature (temp)) from Baseline to Week 4, Week 8 and Week 12 for MC2-25 cream compared to MC2-25 vehicle.

Shift in frequencies of clinically significant and not clinically significant vital signs values from Baseline to Week 4, Week 8 and Week 12 for MC2-25 cream compared to MC-25 vehicle.

- Mean change in laboratory assessments (biochemistry and hematology) from Baseline to Week 4 and Week 12 for MC2-25 cream compared to MC2-25 vehicle. Shift in frequencies of normal, abnormal and abnormal clinically significant or not clinically significant laboratory values from Baseline to Week 4, Week 8 and Week 12 for MC2-25 cream

compared to MC-25 vehicle.

- Shifts in physical examination from Baseline to Week 12 by body area will be displayed. Frequencies of normal, abnormal and abnormal clinically significant and abnormal clinically not significant values of physical examination from Baseline to Week 12 for MC2-25 cream compared to MC-25 vehicle.
- Shifts in electrocardiograms (ECGs) from Baseline to Week 4 and Week 12 will be displayed. Frequencies of normal, abnormal and abnormal clinically significant and abnormal clinically not significant values from Baseline to Week 4 and Week 12 for MC2-25 cream compared to MC-25 vehicle.
- Percentage of subjects who missed 1 or more dialysis visits during the Double-blind Treatment Period as recorded on end of trial visit. Not applicable (NA) category will be presented for subjects not on dialysis.

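### SAP 5.6.4, as most naturally read, drops the protocol's four-level relationship summary, so unlikely-related events cannot be separated from the related counts, and the protocol's ADR endpoint is left undefined

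*SAP*

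**What the plan says.** **Counting rule.** Protocol 8.7.1: "An AE is related if relationship to trial product is not assessed as unrelated". SAP 5.6.4 spells out the same set: "An AE is related if relationship to IMP is assessed as unlikely related, probably related, or possibly related". SAP 3.5 repeats it in the endpoint list: "treatment-related TEAEs (unlikely related, probably related, and possibly related". The rule also governs the related serious TEAEs.

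**Meaning of the grade.** Protocol 7.12.4 has four grades. For *unlikely related* it says that "the temporal relationship of the AE to IMP administration makes a causal relationship unlikely" and that "other concomitant medication, therapeutic interventions or underlying disease provide plausible explanations for the observed AE".

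**Relationship summary.** Protocol 8.7.1 asks for TEAEs to be summarised "by relationship to trial product (not related, unlikely, possibly, or probably", which is four levels. SAP 5.6.4 plans the summary "by relationship to IMP [not related or related (unlikely related, possibly related and probably related".

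**ADRs.** The protocol synopsis and section 4.2 name ADR frequency among the safety endpoints. The abbreviation list expands the term, but neither document defines it. SAP 3.5 has no ADR endpoint; treatment-related TEAEs stand at that place in its list.

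**Changes from the protocol.** SAP section 1 undertakes to explain changes from the protocol's methods. SAP 6.2 lists two: the added 70% threshold for complete response and the deleted biopsy analysis.

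**The concern.** A related row built on this rule mixes two kinds of event: those the investigator attributed mainly to something else, and those for which a causal link could not be dismissed. Under protocol 8.7.1 this does little harm, because the four-level table lets the reader take the unlikely grade out again. If the SAP shows only two levels, no planned summary table does that.

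This is the first clinical trial of the cream. Protocol Table 1 says application-site reactions in humans cannot be ruled out, and protocol 2.3 describes the population as frail. A reader will look to the related-TEAE and related-TESAE rates for the first estimate of how often the cream causes reactions. If many unlikely-related events unconnected with treatment enter both arms, those overall rates overstate reactions and understate the contrast between cream and vehicle. The protocol's ADR endpoint, which could have supplied a narrower count, has no definition and no table.

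**Working it through.** The documents give no figure to reproduce, so the check is a comparison of texts followed by an illustration.

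**1. Texts side by side**

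| Item | Protocol | SAP |
|---|---|---|
| Events counted as related | All except not related (8.7.1) | Unlikely, possibly, probably (3.5, 5.6.4): the same set |
| Levels in the relationship summary | Four (8.7.1) | Two on the natural reading, with the three related grades named in a bracket (5.6.4) |
| ADR endpoint | Named, not defined (synopsis, 4.2) | Not listed; treatment-related TEAEs instead (3.5) |
| Change recorded | – | Not in 6.2 |

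The counting rule agrees between documents. The summary layout and the endpoint list do not.

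**2. Direction of the effect**

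Let *r* be the proportion of subjects with a possibly or probably related TEAE, and *b* the proportion with an unlikely-related TEAE. Assume *b* is equal in both arms and independent of *r*. The proportion with any related TEAE under the broad rule is

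1 − (1 − r)(1 − b).

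This is never below *r*. The difference between arms becomes (1 − b)(r_cream − r_vehicle), so it shrinks by the factor (1 − b), and the risk ratio moves towards 1.

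**3. Illustration**

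The arm sizes, 72 and 36, are from protocol 8.2. All rates are assumptions: r = 15% on cream and 5% on vehicle.

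| b | Cream | Vehicle | Difference | Risk ratio |
|---|---|---|---|---|
| 0% | 15.0% | 5.0% | 10 points | 3.00 |
| 10% | 1 − 0.85 × 0.90 = 23.5% | 1 − 0.95 × 0.90 = 14.5% | 9 points | 1.62 |
| 20% | 1 − 0.85 × 0.80 = 32.0% | 1 − 0.95 × 0.80 = 24.0% | 8 points | 1.33 |
| 30% | 1 − 0.85 × 0.70 = 40.5% | 1 − 0.95 × 0.70 = 33.5% | 7 points | 1.21 |
| 40% | 1 − 0.85 × 0.60 = 49.0% | 1 − 0.95 × 0.60 = 43.0% | 6 points | 1.14 |

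In expected subjects, the first row is 72 × 0.15 = 10.8 versus 36 × 0.05 = 1.8. The row for b = 30% is 72 × 0.405 = 29.2 versus 36 × 0.335 = 12.1.

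Two other assumed pairs, 20% versus 5% and 10% versus 3%, were run over the same values of b. Across all three pairs, risk ratios of 3.0 to 4.0 fall to between 1.10 (10% versus 3%, b = 40%) and 1.93 (20% versus 5%, b = 10%). The ratio moves far more than the difference, so both should be read together.

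**The case against.** **The broad rule is the protocol's own.** A reader might infer that the SAP widened the definition of related. It did not: protocol 8.7.1 sets the same rule, and it was specified in advance. For a cream new to humans, counting everything not ruled out is defensible, because it catches reactions that an investigator under-attributes. Replacing the rule in the SAP alone would make the SAP conflict with the protocol. This objection stands in full, and the broad set should stay.

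**The SAP bracket may mean sub-rows.** It names all three related grades, and the SAP keeps the protocol's rule of counting a subject once under the strongest relationship. This stands in part. Two levels is the natural reading, but not the only one, and two programmers could build different tables from it.

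**Background events need not land in the unlikely grade.** Protocol 7.12.4 places an event in *not related* when an underlying condition explains it sufficiently. A reader might infer that background kidney-disease events will dominate the related count; the documents give no AE rates and do not support that.

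**A signal would still be visible.** Related TEAEs are also tabulated by SOC and preferred term, where events of other kinds cannot dilute an application-site term. The all-TEAE tables by SOC and preferred term, and the severity tables, do not use the relationship grade. TEAEs are listed by subject, and relationship is collected for each AE (protocol 7.12.1). SAP 5.6 limits safety to descriptive statistics, so no test is affected. All of this stands, and it confines the point to the overall related-TEAE and related-TESAE rates and the relationship table.

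**ADR may simply mean related TEAE.** Protocol 8.7.1 itself summarises related TEAEs rather than ADRs, and nothing shows that possibly or probably related was intended. That is correct. It is also why the term needs a definition.

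**Conclusion.** The point holds as a reporting gap. Both documents count unlikely-related events as related; the protocol's four-level summary lets a reader undo that. On its natural reading the SAP removes the summary without recording the change, and the protocol's ADR endpoint has neither a definition nor a table.

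The consequence is conditional. Inflated rates and a diluted contrast require unlikely-related events to be common, similar in both arms and mostly not caused by the product. Under those assumptions, with b from 10% to 40%, the difference in the overall related rate shrinks by 10% to 40% of its value, and the ratio falls as shown in the table. If real reactions were graded unlikely, the broad set would be the more informative one. The documents do not support the stronger claim that the reported reaction rate is in fact inflated or that a signal is in fact hidden. This is a cheap improvement that affects no efficacy result and no test.

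**What to change.** 1. In SAP 5.6.4, state that TEAEs are tabulated at all four relationship levels, as protocol 8.7.1 plans.
2. In SAP 3.5 and 5.6.4, add a labelled ADR row, defined as possibly or probably related TEAEs, with the serious ones shown separately. Place it beside the protocol's broad related set, which stays unchanged.
3. In SAP 6.2, record the ADR definition and any remaining departure from protocol 8.7.1. If two levels really are intended, list that there with the reason.

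The cost is a few lines of SAP wording and one or two extra table rows. No new data are needed. Keeping both sets avoids a conflict with the protocol and lets readers see how much of the related count comes from the unlikely grade.
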